Proportion of subjects who obtain a response as defined by IWG 2006 criteria with a baseline *TP53* VAF $\geq 20\%$ versus $< 20\%$ or high versus low nuclear p53 protein expression

Correlation of *TP53* VAF with nuclear p53 protein expression as determined by IHC

Proportion of subjects who achieve $\geq 50\%$ reduction in *TP53* VAF

Progression free survival (PFS) and OS in clonal responders ($\geq 50\%$ reduction in *TP53* VAF) versus non-responders

Profile expression of genes related to p53-mediated signal transduction before and after APR-246 treatment

Profile ROS production before and after APR-246 treatment

AML transformation according to World Health Organization (WHO) criteria

OS

LFS

Determine recurrent gene mutations in *ASXL1*, *BCOR*, *BRAF*, *CALR*, *CBL*, *CEBPA*, *CSF3R*, *DNMT3A*, *ETV6*, *EZH2*, *GATA2*, *GNAS*, *IDH1*, *IDH2*, *JAK2*, *KIT*, *KRAS*, *MPL*, *NF1*, *NPM1*, *NRAS*, *PDGFRA*, *PDGFRB*, *PHF6*, *PTPN11*, *RAD21*, *RUNX1*, *SETBP1*, *SF3B1*, *SMC1A*, *SMC3*, *SRSF2*, *STAG2*, *STAT3*, *STAT5b*, *TET2*, *TP53*, *U2AF1*, *WT1*, and *ZRSR2* at study entry and serially throughout treatment to assess changes in somatic mutation landscape

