We have recently analyzed our own experience on molecularly profiled patients at Moffitt Cancer Center and identified that the clonal burden, or variant allele frequency (VAF), had significant impact on clinical phenotype and more importantly further stratified prognosis over binary mutational analysis alone and/or clinical prognostic models¹⁹. Specifically, MDS patients with a *TP53* VAF > 40% had a median overall survival (OS) of 124 days versus an OS that was not reached in patients with VAF < 20% (hazard ratio (HR), 3.52; $P = 0.01$) with validation in an independent cohort (HR, 4.94, $P = 0.01$). Overall, *TP53* mutant MDS and AML patients have a median OS ranging from 5-9 months with 8 months representing the best estimate when restricting to MDS and oligoblastic AML (20-30% blasts)^{9,19-22}. Together, these data highlight the dismal outcomes of *TP53* mutant patients and the dire need for the development of novel therapeutic strategies, particularly in this patient population.

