- i. Duration of response defined as the time between achieving response and progression of disease.
- ii. OS at 8 months
- iii. Proportion of subjects achieving hematological improvement (HI), partial response (PR), complete response (CR), and/or marrow CR (mCR) by the IWG 2006 criteria (see appendix B)
- iv. Proportion of subjects who obtain a response as defined by IWG 2006 criteria with a baseline *TP53* VAF $\geq 20\%$ versus $< 20\%$ or high versus low nuclear p53 protein expression

- v. Correlation of *TP53* VAF with nuclear p53 protein expression as determined by IHC
- vi. Proportion of subjects who achieve $\geq 50\%$ reduction in *TP53* VAF.
- vii. Progression free survival (PFS) and OS in clonal responders ($\geq 50\%$ reduction in *TP53* VAF) versus non-responders
- viii. Profile expression of genes related to p53-mediated signal transduction before and after APR-246 treatment
- ix. Profile ROS production before and after APR-246 treatment
- x. AML transformation according to World Health Organization (WHO) criteria
- xi. OS
- xii. LFS
- xiii. Determine recurrent gene mutations in *ASXL1*, *BCOR*, *BRAF*, *CALR*, *CBL*, *CEBPA*, *CSF3R*, *DNMT3A*, *ETV6*, *EZH2*, *GATA2*, *GNAS*, *IDH1*, *IDH2*, *JAK2*, *KIT*, *KRAS*, *MPL*, *NF1*, *NPM1*, *NRAS*, *PDGFRA*, *PDGFRB*, *PHF6*, *PTPN11*, *RAD21*, *RUNX1*, *SETBP1*, *SF3B1*, *SMC1A*, *SMC3*, *SRSF2*, *STAG2*, *STAT3*, *STAT5b*, *TET2*, *TP53*, *U2AF1*, *WT1*, and *ZRSR2* at study entry and serially throughout treatment to assess changes in somatic mutation landscape.

Preliminary data on the above endpoints will prove to be very useful for further investigation of this protocol's treatment. Such data will be summarized appropriately in an exploratory fashion. Both point estimates and 95% confidence intervals will be reported, if feasible. Time-to-event endpoints such as OS and LFS will be summarized using the Kaplan-Meier product-limit method.

16. Laboratory Correlates

Unless otherwise specified, all laboratory correlates will be performed in the laboratory of [name] or at Genoptix medical laboratory.

1. Mutation analyses

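### Baseline TP53 VAF, reported by the protocol as strongly prognostic, enters no planned survival analysis; the exploratory clonal-responder PFS/OS comparison may be confounded, and 8-month OS depends on VAF mix

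*Combined protocol and SAP*

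**What the plan says.** Section 2.2 describes VAF as refining prognosis beyond mutation status and clinical scores. In the institution's series, patients with VAF above 40% "had a median overall survival (OS) of 124 days versus an OS that was not reached" when VAF was below 20%, with a hazard ratio of 3.52. An independent cohort gave 4.94. Both carry P = 0.01, and nothing is given for 20-40%. The same section puts historical median OS at 5-9 months, "with 8 months representing the best estimate when restricting to MDS and oligoblastic AML (20-30% blasts").

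Baseline VAF is to be measured by the central laboratory in all patients (Sections 5 and 16.1), and eligibility sets no VAF floor (Section 4.1). Section 15.4 uses it in two places:
- endpoint iv: "Proportion of subjects who obtain a response as defined by IWG 2006 criteria with a baseline" VAF of at least 20% versus less;
- endpoint v: correlation with p53 immunohistochemistry.

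Endpoint vii is "Progression free survival (PFS) and OS in clonal responders" (a VAF fall of at least 50%) versus non-responders. The only survival method named is this: "Time-to-event endpoints such as OS and LFS will be summarized using the Kaplan-Meier product-limit method". Section 15.2 splits efficacy by dose cohort only. No covariate, stratum or model is named for any survival endpoint. The synopsis and Section 15.4 both treat these secondary analyses as exploratory.

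**The concern.** Objective 1.3.7 asks whether clonal suppression goes with better outcomes. Responder status is a ratio whose denominator is baseline VAF, and baseline VAF is itself tied to survival. If the two groups start from different VAF levels, part or all of a PFS or OS difference can reflect starting burden rather than suppression. An unadjusted Kaplan-Meier contrast cannot separate the two.

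The same factor affects the single-arm survival figure. The 8-month time point matches the historical median in Section 2.2, which makes that median the natural yardstick. With no VAF limit at entry, the proportion alive at 8 months can rise or fall with the share of low-VAF patients and no drug effect at all. Section 15.4 expects these data to inform further study of the regimen, so a misattributed difference could carry forward.

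**Working it through.** **The plan's own figures.** No survival endpoint has a sample size, power or target, so there is none to reproduce. The CR design does reproduce (power 0.900, early termination 0.656, one-sided type I error 0.048) and is not in question.

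**Inputs from the documents.** Median OS at VAF >40% is 124 days. The hazard ratio H for >40% versus <20% is 3.52 or 4.94. The historical median is 8 months, and n = 45.

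**Assumptions, not in the documents.** Exponential survival; the VAF shares; a 20-40% hazard at the geometric midpoint of the other two bands; and any link between baseline VAF and clonal response.

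**1. Clonal-responder comparison with no true effect.** Take two VAF groups (>40% and <20%), with high-VAF share *a* in responders and *b* in non-responders. The starting hazard ratio, responder versus non-responder, is (aH + 1 − a)/(bH + 1 − b).

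| a / b | H = 3.52 | H = 4.94 |
|---|---|---|
| 50% / 50% | 1.00 | 1.00 |
| 40% / 60% | 2.008/2.512 = 0.80 | 2.576/3.364 = 0.77 |
| 30% / 70% | 1.756/2.764 = 0.64 | 2.182/3.758 = 0.58 |
| 60% / 40% | 2.512/2.008 = 1.25 | 3.364/2.576 = 1.31 |

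A Cox model on 80,000 simulated patients censored at 2 years agrees. Its non-responder versus responder ratios of 1.25/1.31, 1.55/1.73 and 0.79/0.76 invert to 0.80/0.76, 0.65/0.58 and 1.27/1.32. With VAF group in the model the ratio is 0.98-1.01.

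At trial size, the simulations take 45 patients, 20/30/50% in the <20/20-40/>40% bands, and status fixed at C3D22. About 33 patients are then at risk, with about 22 events. Across different codings of the gradient:
- response probability falling from 65% to 35% as VAF rises: unadjusted hazard ratio 0.74-0.84;
- falling from 80% to 20%: 0.54-0.72, with 10-24% false positives at a nominal 5%;
- gradients reversed: 1.17-1.73;
- no gradient: 0.98-1.00;
- adjusted for baseline VAF: 0.94-1.02, with 5-6% false positives.

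**2. 8-month OS by VAF.**
- VAF >40%: 8 × 30.4375 = 243.5 days, so 0.5^(243.5/124) = 0.256.
- VAF <20%: 0.256^(1/3.52) = 0.68, or 0.256^(1/4.94) = 0.76.
- VAF 20-40% (midpoint assumption): 0.679^√3.52 = 0.48, or 0.759^√4.94 = 0.54.

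Now change the mix from 10/30/60% to 40/30/30% (<20/20-40/>40%):
- H = 3.52: 0.1(0.679) + 0.3(0.484) + 0.6(0.256) = 0.37, rising to 0.4(0.679) + 0.3(0.484) + 0.3(0.256) = 0.49.
- H = 4.94: from 0.39 to 0.54 by the same sum.

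The middle share is constant, so the shift does not depend on the midpoint assumption: 0.3 × (0.679 − 0.256) = 0.127, and 0.3 × (0.759 − 0.256) = 0.151.

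**3. Anchored to the historical median.** With two groups, a 50/50 mix and overall 8-month OS set to 50%, moving the high-VAF share from 30% to 70% takes 8-month OS from 58% to 42% (H = 3.52) or from 60% to 40% (H = 4.94).

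**4. Yardstick.** The exact 95% interval for 23/45 is 36% to 66%, a half-width of about 15 points.

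**The case against.** **Confounding is not demonstrated.** A reader might infer from the prognostic hazard ratios that the comparison is confounded. That also needs baseline VAF to differ between responders and non-responders, and no section links baseline VAF to the chance of a 50% fall. A shared denominator, objective 1.3.4 and the VAF-expression link in Section 2.3 make a link plausible but establish neither its existence nor its sign. This objection stands.

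**The sizes rest on invented inputs.** The gradients and VAF shares are assumed. In the moderate gradient the bias is about 0.25 on the log scale against a standard error of about 0.44. The hazard ratios are imprecise: if P = 0.01 is a two-sided Wald value (an assumption), exp(ln H ± 1.96 × ln H/2.576) gives about 1.4-9.2 and 1.5-16.7. They contrast the extremes and do not apply at the plan's 20% cut. The base mix in the model (20/30/50%) gives 8-month OS of 41-44%, not the 50% that an 8-month median implies. All of this stands as a limit on the numbers, though the anchored version shows a swing of similar order.

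**The plan claims little.** Objective 1.3.7 asks about correlation. Neither endpoint has a test, threshold or decision rule, and no section formally compares 8-month OS with history. This stands and limits the consequence. It does not show why a prognostic factor that the protocol itself highlights, and already measures, should be left out.

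**Adjustment buys little.** On a 20% share the <20% band holds about 9 patients, and the exact interval for 6/9 is 30-93%. A linear VAF term is a modelling choice, and Section 13 allows marrow instead of blood VAF for some patients. These are fair cautions, but they are reasons to keep the analysis descriptive rather than to omit it.

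**Conclusion.** The omission is real and worth correcting, as an improvement to exploratory analyses. Endpoint vii may be confounded by baseline VAF, in either direction. With no true effect the unadjusted hazard ratio is roughly 0.55-0.84 or 1.17-1.73 under the assumed imbalances, 1.0 with balance, and about 1.0 once VAF is in the model. The 8-month OS figure depends on VAF mix by 13-15 points for a large assumed change, similar to its own sampling error.

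Three stronger readings are not supported. VAF cannot be called the strongest known survival predictor: Section 2.2 gives mutational status that rank and says only that VAF refines it. The 4.94 is not the institution's own result. And the trial's main conclusion is not at risk, because the CR rule does not use these endpoints.

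Guarantee-time bias, from defining responders on treatment with no landmark named, is a separate issue that adjustment for baseline VAF does not remove.

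**What to change.** In Section 15.4, labelled exploratory:

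1. For endpoint vii, add a Cox model for PFS and for OS with clonal-responder status and continuous baseline TP53 VAF as covariates, reported beside the Kaplan-Meier curves.
2. Show the baseline VAF distribution, and report OS and 8-month OS descriptively by baseline VAF band (<20%, 20-40%, >40%) with the overall figure, particularly if it is read against the historical 8-month median.

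The cost is two sentences and a few lines of analysis; no new data or patients are needed. With about 20 events the adjusted interval may be slightly wider if responder status and VAF are strongly related, and the band estimates will be imprecise. If the two are unrelated, adjustment does no harm: in simulation with a true hazard ratio of 0.4, power went from about 36% to 42%. Specifying the model now avoids choosing it after the data are seen.

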1. OBJECTIVES

1.1. Primary Objective (Phase 1b):

1.1.1. To determine the safe and recommended Phase 2 dose (RP2D) of APR-246 in combination with azacitidine as determined by dose-limiting toxicities (DLTs)

1.2. Primary Objective (Phase 2):

1.2.1. To determine the proportion of patients with *TP53* mutant myeloid neoplasms who are in complete remission as measured by the international working group criteria (IWG 2006)

1.3. Secondary Objectives:

1.3.1. To determine the duration of response

1.3.2. To determine the proportion of patients with *TP53* mutant myeloid neoplasms alive at 8 months

1.3.3. To determine overall best response rates as measured by the international working group criteria (IWG 2006)

1.3.4. To determine if mutant TP53 variant allele frequency (VAF) or p53 protein expression predicts response to APR-246 with azacitidine

1.3.5. To determine if p53 protein expression correlates with TP53 VAF

1.3.6. To determine if APR-246 with azacitidine treatment leads to mutant TP53 clonal suppression

1.3.7. To determine if TP53 clonal suppression correlates with outcomes.

1.3.8. To determine if APR-246 treatment upregulates p53 target genes

1.3.9. To determine if APR-246 induces reactive oxygen species (ROS) production

1.3.10. To determine the rate and time to acute myeloid leukemia (AML) transformation

1.3.11. To determine the median overall survival (OS)

1.3.12. To determine whether recurrent genetic mutations are predictive of response

2. BACKGROUND

2.1. Myelodysplastic Syndromes

Myelodysplastic syndromes (MDS) are a heterogeneous group of neoplasms arising from a clonal hematopoietic precursor^{1,2}. MDS is characterized clinically by cytopenias and a tendency to transform to acute myeloid leukemia (AML)³. Prognostic scoring systems have been

developed to help stratify patients based on predicted survival and progression to AML³⁻⁵. In practice, treatment decisions are made by grouping patients with MDS into lower and higher risk subgroups as defined by clinical prognostic scoring systems. Specifically, the International Prognostic Scoring System (IPSS) and its more modern version, the revised-IPSS (RIPSS), represent the most widely used clinical prognostic tools^{3,4}. Those patients that fall in the higher risk group have an expected survival of less than 12 months if left untreated and progress to AML greater than 30% of the time.

2.2. TP53 Mutations in MDS and AML

The advent of next generation sequencing (NGS) has provided a rapid and efficient platform for genome studies that has revolutionized the diagnostic, prognostic, and therapeutic realms of myeloid malignancies⁶. Current NGS myeloid panels incorporate 20-50 genes and can identify mutations in the vast majority of patients^{7,8}. In MDS, mutations of *ASXL1*, *ETV6*, *EZH2*, *RUNX1* and *TP53* were found to be independently associated with decreased survival⁹. Of these, recent investigations have suggested that the mutational status of *TP53* is the most important negative prognostic factor in MDS patients. To date, the only disease modifying agents in MDS include lenalidomide in patients with isolated deletion of 5q (del(5q)) and azacitidine (a DNA methyltransferase (DNMT) inhibitor/hypomethylating agent (HMA)) in MDS patients with higher risk disease (i.e., intermediate 2/high risk by IPSS and high/very-high by RIPSS). Lenalidomide was approved based on the MDS-003 trial with 67% of del (5q) patients achieving transfusion independence and 45% of patients with complete cytogenetic response¹⁰. However, primary resistance to lenalidomide has been directly linked to *TP53* mutation which occurs in 20% of patients¹¹. Whereas partial cytogenetic responses occur in up to 73% of patients, *TP53* mutated del(5q) patients only have cytogenetic responses in 0-11% of cases¹²⁻¹⁴. For higher risk MDS patients, azacitidine represents the standard of care based on the AZA-001 trial that demonstrated a survival advantage for azacitidine when compared with induction chemotherapy, low dose cytarabine, or best supportive care (24.5 months versus 15 months, $p < 0.0001$)¹⁵. A recent study in MDS showed strong association of *TP53* mutation with poor outcome in azacitidine treated patients¹⁶. In addition, Bejar and colleagues recently confirmed decreased OS in *TP53* mutated MDS patients treated with HMA without effect on response rates¹⁷. Lastly, mutations of *TP53* strongly predict for lack of benefit to allogeneic bone marrow transplantation,

which represents the only curative option for patients with MDS¹⁸. This study highlights the prognostic importance of *TP53* mutations as patients with complex karyotype without *TP53* mutation had similar survival to patients with normal karyotype.

We have recently analyzed our own experience on molecularly profiled patients at Moffitt Cancer Center and identified that the clonal burden, or variant allele frequency (VAF), had significant impact on clinical phenotype and more importantly further stratified prognosis over binary mutational analysis alone and/or clinical prognostic models¹⁹. Specifically, MDS patients with a *TP53* VAF > 40% had a median overall survival (OS) of 124 days versus an OS that was not reached in patients with VAF < 20% (hazard ratio (HR), 3.52; $P = 0.01$) with validation in an independent cohort (HR, 4.94, $P = 0.01$). Overall, *TP53* mutant MDS and AML patients have a median OS ranging from 5-9 months with 8 months representing the best estimate when restricting to MDS and oligoblastic AML (20-30% blasts)^{9,19-22}. Together, these data highlight the dismal outcomes of *TP53* mutant patients and the dire need for the development of novel therapeutic strategies, particularly in this patient population.

2.3. APR-246

Restoration of wild type function from mutant or otherwise dysfunctional/unfolded p53 has been suggested to be an efficient strategy for selective elimination of tumor cells²³. A molecule that reactivates mutant p53 should be less effective in cells with wild type p53 because the wild type protein is found at low levels in the absence of stress. In contrast, mutant p53 often accumulates at high levels and is already “pre-activated” by posttranslational modifications in tumor cells—due to constitutive stress signaling, i.e., oncogene activation, DNA damage, and hypoxia. This has been commonly observed in MDS with *TP53* mutation and we have recently shown that *TP53* VAF directly correlates with p53 expression in analysis of bone marrow from *TP53* mutant patients²⁴. Therefore, mutant p53 reactivation should trigger robust apoptosis in tumor cells but not in normal cells²⁵.

Wiman and colleagues identified APR-017 (also called PRIMA-1) in a cellular screen for compounds that induce apoptosis preferentially in human tumor cells expressing exogenous mutant p53²⁶. The effect of APR-017 was more pronounced in AML cells with homozygous *TP53* deletions than in wild type *TP53* cells, while commonly used anti-leukemic drugs showed

the opposite pattern, being less pronounced in AML cells with abnormal chromosome 17²⁷. The optimization program of the lead compound APR-017 resulted in the identification of the structural analogue APR-246, Aprea's candidate drug in clinical development²⁸. APR-246 has more drug-like properties in comparison to APR-017, e.g., being more potent and showing better cellular permeability²⁹.

2.4. Mechanism of action of APR-246

APR-246 (like the parent compound APR-017) is a prodrug, which under physiological conditions is spontaneously converted to methylene quinuclidinone (MQ), a Michael acceptor that binds covalently to cysteines in mutant p53³⁰. Transfer of MQ-modified mutant p53 protein into tumor cells lacking p53 induced massive apoptosis, indicating that covalent binding of MQ per se is sufficient to activate mutant p53 and induce a p53 dependent biological response. These and other experiments directly looking at the conformational state of p53 protein have confirmed that binding of MQ pushes unfolded mutant or wild type p53 towards a functional wild type conformation. MQ is a 'soft' electrophile, hence strongly preferring 'soft' nucleophiles such as thiols. Once formed from APR-246, MQ could potentially bind to cysteines in many proteins in the cell. However, various factors may limit the number of protein targets, including accessibility of the thiol, nucleophilicity of the sulfur, and structural flexibility of the targeted protein domain.

Thioredoxin reductase 1 (TrxR1) was identified as a target of MQ, potentially contributing to the anti-cancer effect³¹. MQ converts this enzyme from a reductase to an oxidase that can produce reactive oxygen species (ROS). This may contribute to APR-246-induced cell death and probably accounts, at least in part, for the observed effects of APR-246 in *TP53* null cancer cells. Further *in vitro* experiments have shown that MQ readily reacts with glutathione, a central molecule in the cellular redox system^{28,32}. Thus, APR-246 via MQ has effects that lead to impairment of the tumor cells capacity to handle oxidative stress, including depletion of glutathione¹³. In tumor cells, the redox system is pushed to the limit of its capacity, while coping with enhanced oxidative stress compared with normal cells, making the redox system an Achilles' heel of tumor cells. This set of properties constitutes synthetically lethal targets which may be utilized to selectively kill tumor cells. The dual activity of APR-246 restoring wt p53 function of mutant p53 and increasing oxidative stress is illustrated in **Figure 1**.

[figure not shown]

Figure 1: Mechanism of action of APR-246 leading to induction of apoptosis.

2.5. APR-246 in Solid and Hematologic Malignancies

This first in human study was a multicenter, open label, non-comparative, Phase I/II dose escalating study of APR-246 infusions in patients with refractory hematological malignancies or prostate cancer (APR-246-01)³³. The study assessed the safety, tolerability, pharmacokinetics and pharmacodynamics of multiple escalating doses of APR-246. An extension of this clinical trial has been conducted with the main objective to evaluate safety at an optimal dose in a more homogenous patient population (see below). The patients received APR-246 on 4 consecutive days as a 2-hour daily intravenous (IV) infusion. Dosing was conducted with three patients at each dose level. The first dose level was 2 mg/kg and was followed by 3, 10, 30, 60 and 90 mg/kg. The treatment phase was followed by a 17 days follow-up phase to reveal any late adverse effects. The HFD was defined as the dose expected to result in maximal plasma concentration (C_{max}) close to but not exceeding 110 µg/mL in any single patient without showing signs of dose limiting toxicity (DLT), or the dose level below the dose where DLT occurred, whichever came first. In total 22 patients, 4 (18.2 %) female and 18 (81.8 %) male with an average age of 67.0 years were enrolled into the study. The indications for the 22 included

patients were acute myeloid leukemia (AML) (7 patients), prostate carcinoma (7 patients), non-Hodgkin's lymphoma (NHL) (4 patients), chronic lymphocytic leukemia (CLL) (3 patients) and multiple myeloma (MM) (1 patient). Eighteen (18) patients completed the study, i.e., completed the day 21 visit and 4 patients were prematurely discontinued.

In regards to activity, the apoptosis pattern in patients with hematological malignancies showed cell cycle changes compatible with cell cycle arrest in all patients with non T-cell malignancy³³. Also, other apoptosis markers were affected such as increased staining for Annexin-V, up regulation of BAX (Bcl-2 associated X protein), NOXA and PUMA expression and up regulation of DcR2 (decoy receptor 2, a marker considered to be associated with senescence). The one responding patient in the initial phase 1 clinical trial was the only *TP53* mutant AML patient. Specifically, this patient had a reduction of blast cell count from 46% to 26% and showed activation of p53 targets supporting in vivo activity.

